5.1.3. Solicited Safety Set

The solicited Safety Set will include all subjects who received at least one dose of study vaccine and had solicited safety data.

5.1.4. Per-Protocol Set for analysis of immunogenicity and efficacy (PPS for analysis of immunogenicity and efficacy)

The PPS for analysis of immunogenicity and efficacy will include all subjects included in the ITTS who fulfilled all eligibility criteria and received all vaccinations according to protocol procedures within the protocol specified intervals, did not use any medication, vaccine or blood products forbidden by the protocol, did not report any underlying medical condition influencing the efficacy response, had available data concerning immunogenicity endpoint measures, and underwent *P. falciparum* challenge. This will include subjects for whom assay results are available for antibodies against at least one study vaccine antigen after vaccination.

5.1.5. Adapted Per-Protocol Set for analysis of efficacy (Adapted PPS for analysis of efficacy)

The Adapted PPS for analysis of efficacy will include all subjects included in the ITTS who fulfilled all eligibility criteria and received all vaccinations according to protocol procedures within the protocol specified intervals and underwent *P. falciparum* challenge.

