11.2.5. Safety

- Handling of missing data: subjects who missed reporting symptoms (unsolicited or concomitant medications) will be treated as subjects without symptoms (unsolicited or concomitant medications, respectively). In case of significant non-compliance of study procedures for reporting symptoms, the analysis plan will be reassessed to ensure more accurate reporting of study data by further analysis.
- For the analysis of solicited symptoms, missing or non-evaluable measurements will not be replaced. Therefore the analysis of the solicited symptoms based on the ES will include only subjects/doses with documented safety data (i.e. symptom screen/sheet completed).
- For a given subject and the analysis of solicited symptoms within 7 days post-vaccination, missing or non-evaluable measurements will not be replaced. Therefore the analysis of the solicited symptoms based on the ES will include only vaccinated subjects for doses with documented safety data (i.e., symptom screen completed). More specifically the following rules will be used:
 - Subjects who documented the absence of a solicited symptom after one dose will be considered not having that symptom after that dose.
 - Subjects who documented the presence of a solicited symptom and fully or partially recorded daily measurement over the solicited period will be included in the summaries at that dose and classified according to their maximum observed daily recording over the solicited period.
 - Subjects who documented the presence of a solicited symptom after one dose without having recorded any daily measurement will be assigned to the lowest intensity category at that dose (i.e., 37.5°C for fever or grade 1 for other symptoms).
 - Doses without symptom sheets documented will be excluded.
- For analysis of unsolicited AEs, such as SAEs or AEs by primary MedDRA term, and for the analysis of concomitant medications, all vaccinated subjects will be considered.
- For the analysis, temperatures will be coded as follows:

Grade	Temperature
0	< 37.5°C (< 99.5°F)
1	≥ 37.5°C (≥ 99.5°F) to ≤ 38.0°C (100.4°F)
2	> 38.0°C (> 100.4°F) to ≤ 39.0°C (102.1°F)
3	> 39.0°C (102.1°F)

- For the analysis, local injection site redness and swelling will be coded as follows:

Grade	Temperature
0	0 mm
1	> 0 to ≤ 50 mm
2	> 50 mm to ≤ 100 mm
3	> 100 mm

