Note that for all tables described in this section, the way the percentage of subjects will be derived will depend on the event analysed (see table below for details). As a result, the N value will differ from one table to another.

Event	N used for deriving % per subject for Vaccination phase	N used for deriving % per dose for Vaccination phase
Concomitant vaccination	All subjects with study vaccine administered	All study visits with study vaccine administered
Solicited general symptom	All subjects with at least one solicited general symptom documented as either present or absent (i.e., symptom screen completed)	All study visits with study vaccine administered and with at least one solicited general symptom documented as either present or absent (i.e., symptom screen completed)
Solicited local symptom	All subjects with at least one solicited local symptom documented as either present or absent (i.e., symptom screen completed)	All study visits with study vaccine administered and with at least one solicited local symptom documented as either present or absent (i.e., symptom screen completed)
Unsolicited symptom	All subjects with study vaccine administered	All study visits with study vaccine administered
Concomitant medication	All subjects with study vaccine administered	All study visits with study vaccine administered

- Related dose: The related dose for an event (e.g., AE, medication, vaccination,...) is the study dose given before an event. In case the event takes place on a day a study dose is given, if the investigator has indicated the timing (before or after the vaccination) the related dose for this event is the most recent study dose given before this event. If the investigator has not indicated the timing, the related dose will be that of the study dose even if the event actually took place before.

Number of decimals displayed:

The following decimal description from the decision rules will be used for demography, efficacy, immunogenicity and safety/reactogenicity results.

Display Table	Parameters	Number of decimal digits
Demographic characteristics	Mean, median age	1
Demographic characteristics	SD (age)	1
Reactogenicity	Mean, Min, Q1, Median, Q3, Max for duration	1
All summaries	p-value	3

Percentages and their corresponding confidence limits will be displayed with:

- no decimals when there are fewer than 50 subjects in each tabulated group
- one decimal when there are at least 50 subjects in at least one tabulated group

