12.4. Reactogenicity and Safety

Template #	Table / Listing Title	Output destination	Template name
Template 19	Compliance in completing solicited adverse events information (Intent-to-treat set)	Post-text	TEX1COMPLIANCE
Template 20	Summary of adverse events (solicited and unsolicited) within 7 days following each vaccination and overall (Intent to treat set)	In-text / Post-text/Synopsis	TAC1LOCGEN
Template 20	Summary of grade 3 adverse events (solicited and unsolicited) within 7 days following each vaccination and overall (Intent to treat set)	Post-text	TAC1LOCGEN
Template 20	Summary of adverse events (solicited and unsolicited) with causal relationship to vaccination within 7 days following each vaccination and overall (Intent to treat set)	Post-text	TAC1LOCGEN
Template 20	Summary of grade 3 adverse events (solicited and unsolicited) with causal relationship to vaccination within 7 days following each vaccination and overall (Intent to treat set)	Post-text	TAC1LOCGEN
Template 20	Summary of adverse events (solicited and unsolicited) within 30 days following each vaccination and overall (Intent to treat set)	Post-text	TAC1LOCGEN
Template 20	Summary of grade 3 adverse events (solicited and unsolicited) within 30 days following each vaccination and overall (Intent to treat set)	Post-text	TAC1LOCGEN
Template 20	Summary of adverse events (solicited and unsolicited) with causal relationship to vaccination within 30 days following each vaccination and overall (Intent to treat set)	Post-text	TAC1LOCGEN
Template 20	Summary of grade 3 adverse events (solicited and unsolicited) with causal relationship to vaccination within 30 days following each vaccination and overall (Intent to treat set)	Post-text	TAC1LOCGEN

CONFIDENTIAL

205081 (MALARIA-092)
Statistical Analysis Plan Amendment 1 Final

Template #	Table / Listing Title	Output destination	Template name
Template 21	Percentage of subject with solicited local symptoms within 7 days following each vaccination and overall (Intent to treat set)	Post-text / Web disclosure	TCEMAX1FRE QSEV
Template 31	Bar graph of the daily prevalence of pain between day 1 and day 7 following each vaccination (Intent to treat set)	Post-text	CEMAX1BARG RAPH
Template 31	Bar graph of the daily prevalence of redness between day 1 and day 7 following each vaccination (Intent to treat set)	Post-text	CEMAX1BARG RAPH

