Template 31	Bar graph of the daily prevalence of swelling between day 1 and day 7 following each vaccination (Intent to treat set)	Post-text	CEMAX1BARG RAPH
Template 21	Percentage of subject with solicited general symptoms within 7 days following each vaccination and overall (Intent to treat set)	Post-text / Web disclosure	TCEMAX1FRE QSEV
Template 31	Bar graph of the daily prevalence of fatigue between day 1 and day 7 following each vaccination (Intent to treat set)	Post-text	CEMAX1BARG RAPH
Template 31	Bar graph of the daily prevalence of gastrointestinal between day 1 and day 7 following each vaccination (Intent to treat set)	Post-text	CEMAX1BARG RAPH
Template 31	Bar graph of the daily prevalence of headache between day 1 and day 7 following each vaccination (Intent to treat set)	Post-text	CEMAX1BARG RAPH
Template 22	Percentage of subjects with temperature by maximum value, within 7 days following each vaccination and overall (Intent to treat set)	Post-text	TCEMAX1TEMP
Template 31	Bar graph of the daily prevalence of temperature between day 1 and day 7 following each vaccination (Intent to treat set)	Post-text	CEMAX1BARG RAPH
Template 30	Summary of subjects taking a concomitant medication within 7-day following each vaccination and overall (Intent to treat set)	Post-text	specific
Template 30	Summary of subjects taking a concomitant medication during the challenge phase (Intent to treat set)	Post-text	specific
Template 23	Summary of subjects with at least one unsolicited adverse event classified by MedDRA Primary System Organ Class and Preferred Term within 30 days of any vaccination (Intention-to-treat set)	Post-text / Web disclosure	TAE1SOCPT
Template 25	Summary of subjects with unsolicited adverse events within 30 days of any vaccination by category (Intention-to-treat set)	Post-text	TAE1SOCPTS UMMARY
Template 23	Summary of subjects with at least one grade 3 unsolicited adverse evens classified by MedDRA Primary System Organ Class and Preferred Term within 30 days of any vaccination (Intention-to-treat set)	Post-text	TAE1SOCPT
Template 23	Summary of subjects with at least one related unsolicited adverse event classified by MedDRA Primary System Organ Class and Preferred Term within 30 days of any vaccination (Intention-to-treat set)	Post-text	TAE1SOCPT

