12.6.4. Reactogenicity and safety

Template 19 Compliance in completing solicited adverse events information (intent-to-treat)

		<Group 1>		<Group 2>		Compliance (%)
		N	n	N	n	
		Compliance (%)		Compliance (%)		
<Vaccination at visit 1>	General solicited adverse events	xxx	xx.x	xxx	xxx	xx.x
		xxx	xx.x	xxx	xxx	xx.x
	Local solicited adverse events	xxx	xx.x	xxx	xxx	xx.x
<Vaccination at visit X>	General solicited adverse events	xxx	xx.x	xxx	xxx	xx.x
		xxx	xx.x	xxx	xxx	xx.x
	Local solicited adverse events	xxx	xx.x	xxx	xxx	xx.x
...		xxx	xx.x	xxx	xxx	xx.x
Per vaccination	...		xx.x	xxx	xxx	xx.x
	General solicited adverse events	xxx				
		xxx				
	Local solicited adverse events	xxx				
		xxx				

Template 20 Incidence and nature of symptoms (solicited and unsolicited) within 7-day following each vaccination and overall (Intention-to-treat set)

	<Group 1>				<Group 2>			
	n	%	95% CI		n	%	95% CI	
			LL	UL			LL	UL
<Vaccination at visit 1> N	xxx				xxx			
Any symptom	xxx	xx.x	xx.x	xx.x	xxx	xx.x	xx.x	xx.x
Local symptom	xxx	xx.x	xx.x	xx.x	xxx	xx.x	xx.x	xx.x
General symptom	xxx	xx.x	xx.x	xx.x	xxx	xx.x	xx.x	xx.x

<Vaccination at visit 2> ...

...

Per subject

Per vaccination

For each dose and overall/subject:

N= number of subjects with at least one administered dose

n/%= number/percentage of subjects presenting at least one type of symptom whatever the study vaccine administered

For overall/dose:

N= number of administered doses

n/%= number/percentage of doses followed by at least one type of symptom whatever the study vaccine administered

95% CI = exact 95% confidence interval, LL = Lower Limit, UL = Upper Limit

Template 21 Incidence of solicited <local/general> symptoms within 7-day following each vaccination and overall (Intention-to-treat set)

Symptom: Xxxxx

	<Group 1>				<Group 2>			
	n	%	95% CI		n	%	95% CI	
			LL	UL			LL	UL
<Vaccination at visit 1> N	xxx				xxx			
Any	xxx	xx.x	xx.x	xx.x	xxx	xx.x	xx.x	xx.x
Related	xxx	xx.x	xx.x	xx.x	xxx	xx.x	xx.x	xx.x
Grade 3	xxx	xx.x	xx.x	xx.x	xxx	xx.x	xx.x	xx.x
Grade 3 related	xxx	xx.x	xx.x	xx.x	xxx	xx.x	xx.x	xx.x
Medically attended visit								

<Vaccination at visit 2> ...

...

Per subject

Per vaccination

For each dose and overall/subject:

N= number of subjects with at least one administered dose

n/%= number/percentage of subjects reporting at least once the symptom

For Overall/dose:

N= number of administered doses

n/%= number/percentage of doses followed by at least one type of symptom

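### The Template 21 footnote counts everyone dosed in N for solicited symptoms, against SAP 11.2.5; rates are understated if sheets are missing and the footnote is followed

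*SAP*

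**What the plan says.** Two parts of the current SAP (Amendment 1) define the denominator for solicited symptoms.

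- **Table shell.** Template 21 in SAP 12.6.4 is titled "Incidence of solicited <local/general> symptoms within 7-day following each vaccination and overall (Intention-to-treat set". For each dose, and for the per-subject overall row, its footnote gives "N= number of subjects with at least one administered dose". For the per-dose overall row it gives "N= number of administered doses".
- **Derivation rules.** SAP 11.2.5 states "Doses without symptom sheets documented will be excluded". Its denominator table sets N for solicited local symptoms, per subject, to "All subjects with at least one solicited local symptom documented as either present or absent (i.e., symptom screen completed". The entry for general symptoms has the same form, and the per-dose entries count vaccination visits with the screen completed. The section also says that N will vary between tables for this reason.

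Protocol 11.6 likewise restricts the solicited analysis to documented subjects and doses, within the total vaccinated cohort.

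The analysis set is not settled either. SAP 5.1.3 defines a new set: "The solicited Safety Set will include all subjects who received at least one dose of study vaccine and had solicited safety data". SAP 5.2.2 gives it an elimination code and section 9 gives a reason for adding it. No table in the 12.4 list and no template in 12.6.4 uses it. The list entries are "Percentage of subject with solicited local symptoms within 7 days following each vaccination and overall (Intent to treat set" and "Percentage of subject with solicited general symptoms within 7 days following each vaccination and overall (Intent to treat set". SAP 11.2.5 names yet another set, ES, which the abbreviation list expands as Exposed Set but section 5 does not define.

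**The concern.** Template 21 shows solicited symptoms only, so its footnote and the 11.2.5 denominators cannot both be followed when a sheet is missing. A programmer working from the shell would keep undocumented doses in N. Such a dose has no record from which a symptom could be counted, so in effect it is scored as symptom-free.

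Reactogenicity by schedule is a secondary objective, and the 2PedFx group receives 1.0 ml at its first two vaccinations where the other groups' full doses are 0.5 ml. Rates on the all-dosed denominator could only be equal to or lower than the documented rates. If diary return differs between schedules, the comparison between them is distorted as well. Both Template 21 tables are marked for web disclosure.

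**Working it through.** **Inputs.** The target is 26 subjects per vaccine group (protocol 11.4). The documents give no symptom rate and no diary-return rate, so there is no figure of the plan's own to reproduce. The number of missing sheets, m = 0 to 5 of 26 (0 to 19%), is an assumption, and the documented rates near 80%, 50% and 20% are illustrative.

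**By-dose rows.** Let x be the number of subjects with the symptom on a completed sheet.

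- Rate under SAP 11.2.5: x / (26 − m)
- Rate under the Template 21 footnote: x / 26
- Ratio, footnote to 11.2.5: (26 − m) / 26, whatever the value of x

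| m | Ratio | Rate near 80% | Rate near 50% | Rate near 20% |
|---|---|---|---|---|
| 0 | 1.00 | 21/26 = 81% in both | 13/26 = 50% in both | 5/26 = 19% in both |
| 1 | 25/26 = 0.96 | 20/25 = 80% v 20/26 = 77% | 12/25 = 48% v 12/26 = 46% | 5/25 = 20% v 5/26 = 19% |
| 2 | 24/26 = 0.92 | 19/24 = 79% v 19/26 = 73% | 12/24 = 50% v 12/26 = 46% | 5/24 = 21% v 5/26 = 19% |
| 3 | 23/26 = 0.88 | 18/23 = 78% v 18/26 = 69% | 12/23 = 52% v 12/26 = 46% | 5/23 = 22% v 5/26 = 19% |
| 5 | 21/26 = 0.81 | 17/21 = 81% v 17/26 = 65% | 10/21 = 48% v 10/26 = 38% | 4/21 = 19% v 4/26 = 15% |

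At m = 5 the loss is about 16 percentage points near 80%, 9 near 50% and 4 near 20%. The exact 95% intervals are wide. For 17/21 the interval is 58% to 95%, and for 17/26 it is 44% to 83%.

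**Per-dose overall row.** The same formula applies to doses. In a three-dose group with everyone dosed there are 3 × 26 = 78 doses. Five missing sheets in total give 73/78 = 0.94. Five missing at each dose give 63/78 = 0.81.

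**Per-subject overall row.** A subject with one completed sheet out of three is in N under both rules. The two denominators differ only by the subjects who have no sheet at all.

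**Would the Solicited Safety Set remove the difference?** It is defined per subject. A subject with a sheet after Dose 1 and none after Dose 2 stays in the set. The set alone therefore does not take the undocumented Dose 2 out of N; only the per-dose exclusion in 11.2.5 does that.

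**The case against.** The strongest reply is that the right denominator is already in the plan. SAP section 6 sends the reader to Annex 1 for derivation rules, and Annex 1 gives documented-only N for solicited symptoms, per subject and per dose. On that view the footnote is a leftover in a table shell. This stands to the extent that dilution is conditional: it happens only if the shell is followed rather than Annex 1. But the SAP does not say which prevails.

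Several stronger readings are tempting, and the documents do not support them.

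- **That the plan has decided to treat a missing diary as no symptom.** No template says so. One sentence of protocol 11.6 does treat unreported symptoms, solicited ones included, as absent, but the next limits the solicited analysis to documented doses. SAP 11.2.5 keeps the limit and drops solicited symptoms from the first rule.
- **That the intent-to-treat label is itself an error.** Protocol 11.6 works within the vaccinated cohort and still counts only documented doses. The label and a documented-only N are compatible.
- **That Template 20 has the same fault.** Its footnote is nearly identical, but it pools solicited and unsolicited events, and 11.2.5 uses all vaccinated subjects for unsolicited symptoms. It lies outside the error.

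The loss may also be small. Protocol 6.6.18 has unreturned diary cards followed up, Template 19 reports compliance, and SAP 11.2.5 provides for reassessing the analysis if non-compliance is significant. SAP section 7 makes all analyses descriptive. These points limit the consequence, but the two denominators still disagree.

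**Conclusion.** The Template 21 footnote contradicts SAP 11.2.5 and the documented-data rule in protocol 11.6, and should be corrected. This is an unresolved inconsistency inside the SAP, demonstrated for Template 21, and not a settled choice of a biased analysis.

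If the footnote is followed, by-dose and per-dose rates are understated by the share of sheets missing, and the per-subject overall rate by the share of subjects with no sheet at all. With 26 dosed and an assumed 1 to 5 sheets missing at a dose, the displayed rate is 0.96 to 0.81 of the documented rate; with none missing the two agree. The comparison is with the documented rate. Whether that rate also holds for subjects who returned no sheet cannot be known from the documents. The unused Solicited Safety Set and the undefined ES belong to the same incomplete alignment. Overall the point is minor.

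**What to change.** - Replace both N definitions in the Template 21 footnote with those of SAP 11.2.5: subjects, or vaccination visits, with the local or general symptom screen completed, as applicable.
- Apply the same N to the solicited temperature table (Template 22) and the daily-prevalence graphs (Template 31). Neither shows an N definition in the text, though the Template 31 example graph was not available to check.
- Keep the per-dose exclusion in 11.2.5 whichever set is chosen.
- Either assign the solicited-only tables to the Solicited Safety Set or delete that set, and replace ES by the name of the set actually used.
- Leave Template 19 on the intent-to-treat set, so that the missing share is visible.

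The cost is SAP wording, footnotes and set labels. No data collection or study procedure changes.

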5.1.2. Intent-to-treat set (ITTS)

The Intent-To-Treat Set (ITTS) will include all subjects who received at least one dose of study vaccine. The ITTS analysis will be performed per treatment actually administered. All challenged infectivity controls will also be included and will be presented as a separate study group.

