6.5. Analysis of safety

6.5.1. Analysis of safety planned in the protocol

The analysis of safety will be performed on the ITTS.

The percentage of subjects with at least one local AE (solicited and unsolicited), with at least one general AE (solicited and unsolicited) and with any AE during the 7-day or 30-day follow-up period after each vaccine dose and overall will be tabulated with exact 95% CI. The percentage of doses followed by at least one local AE (solicited and unsolicited), by at least one general AE (solicited and unsolicited) and by any AE during the 7-day or 30-day follow-up period will be tabulated with exact 95% CI. The same computations will be done for Grade 3 AEs, for any AEs considered related to vaccination and for any Grade 3 AEs considered related to vaccination.

The percentage of subjects reporting each individual solicited local AE (any grade and Grade 3) and each individual solicited general AE (any grade, Grade 3, any related, Grade 3 related, resulting in medically attended visit) during the 7-day follow-up period (Day 0-6) after each vaccine dose and overall will be tabulated for each group. Similarly, the percentage of doses followed by each individual solicited local and general AE will be tabulated, for the overall and for each vaccination course, with exact 95% CI.

For fever (fever is defined as temperature $\geq 37.5^{\circ}\text{C}/99.5^{\circ}\text{F}$ for oral, axillary or tympanic route, or $\geq 38.0^{\circ}\text{C}/100.4^{\circ}\text{F}$ for rectal route), the number and percentage of subjects reporting fever by half degree ($^{\circ}\text{C}$) cumulative increments during the first seven days (Day 0-6) after each vaccine dose and overall will be tabulated. Similar tabulations will be performed for any fever with a causal relationship to vaccination and Grade 3 ($> 39.0^{\circ}\text{C}$) causally related fever. The maximum temperature reported over the 7-day follow-up period (Day 0-6) overall doses will be tabulated.

The percentage of subjects reporting unsolicited AEs within 30 days (Day 0-29) after each vaccine dose (overall doses) and percentage of subjects reporting AEs after the sporozoite challenge will be tabulated by group and by MedDRA preferred term with exact 95% CI. Similar tabulation will be done for Grade 3 unsolicited AEs, for any causally related unsolicited AEs and for Grade 3 causally related unsolicited AEs.

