Template 23	Summary of subjects with at least one grade 3 related unsolicited adverse event classified by MedDRA Primary System Organ Class and Preferred Term within 30 days of any vaccination (Intention-to-treat set)	Post-text	TAE1SOCPT
Template 23	Summary of subjects with at least one unsolicited adverse event classified by MedDRA Primary System Organ Class and Preferred Term within 30 days post- challenge (Intention-to-treat set)	Post-text/ Web disclosure	TAE1SOCPT

CONFIDENTIAL

205081 (MALARIA-092)
Statistical Analysis Plan Amendment 1 Final

Template #	Table / Listing Title	Output destination	Template name
Template 23	Summary of subjects with at least one grade 3 unsolicited adverse event classified by MedDRA Primary System Organ Class and Preferred Term within 30 days post- challenge (Intention-to-treat set)	Post-text	TAE1SOCPT
Template 23	Summary of subjects with at least one related unsolicited adverse event classified by MedDRA Primary System Organ Class and Preferred Term within 30 days post- challenge (Intention-to-treat set)	Post-text	TAE1SOCPT
Template 23	Summary of subjects with at least one grade3 related unsolicited adverse event classified by MedDRA Primary System Organ Class and Preferred Term within 30 days post- challenge (Intention-to-treat set)	Post-text	TAE1SOCPT
Template 25	Summary of subjects with unsolicited adverse events within the 30 days post-challenge by category (Intention-to-treat set)	Post-text	TAE1SOCPTS UMMARY
Template 26	Listing of potential immune mediated disorders (pIMDs) reported as identified by predefined list of preferred terms and/or by investigator assessment (Intention-to-treat set)	Post-text / Web disclosure	TAE1PIMDLIS T
Template 26	Listing of meningitis reported as identified by predefined list of preferred terms and/or by investigator assessment (Intention-to-treat set)	Post-text / Web disclosure	TAE1PIMDLIS T

CONFIDENTIAL

205081 (MALARIA-092)
Statistical Analysis Plan Amendment 1 Final

Template #	Table / Listing Title	Output destination	Template name
Template 23	Summary of subjects with at least one serious unsolicited adverse event classified by MedDRA Primary System Organ Class and Preferred Term within 30 days of any vaccination (Intention-to-treat set)	Post-text/ Web disclosure	TAE1SOCPT

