Template 23	Summary of subjects with at least one serious fatal unsolicited adverse event classified by MedDRA Primary System Organ Class and Preferred Term within 30 days of any vaccination (Intention-to-treat set)	Post-text/ Web disclosure	TAE1SOCPT
Template 23	Summary of subjects with at least one serious related unsolicited adverse event classified by MedDRA Primary System Organ Class and Preferred Term within 30 days of any vaccination (Intention-to-treat set)	Post-text/ Web disclosure	TAE1SOCPT
Template 23	Summary of subjects with at least one serious unsolicited adverse event classified by MedDRA Primary System Organ Class and Preferred Term occurring from Dose 1 (Day 1) until the last study visit (Day 376) (Intention-to-treat set)	Post-text / Web disclosure	TAE1SOCPT
Template 24	Summary of occurrences and subjects with at least one serious unsolicited adverse event classified by MedDRA Primary System Organ Class and Preferred Term occurring from Dose 1 (Day 1) until the last study visit (Day 376) (Intention-to-treat set)	Web disclosure	TAC1SOCPT
Template 23	Summary of subjects with at least one serious fatal unsolicited adverse event classified by MedDRA Primary System Organ Class and Preferred Term occurring from Dose 1 (Day 1) until the last study visit (Day 376) (Intention-to-treat set)	Post-text / Web disclosure	TAE1SOCPT
Template 23	Summary of subjects with at least one serious related unsolicited adverse event classified by MedDRA Primary System Organ Class and Preferred Term occurring from Dose 1 (Day 1) until the last study visit (Day 376) (Intention-to-treat set)	Post-text/ Web disclosure	TAE1SOCPT
Template 23	Summary of subjects with at least one serious unsolicited adverse event classified by MedDRA Primary System Organ Class and Preferred Term occurring from day of challenge until the end of challenge phase (Day 314) (Intention-to-treat set)	Post-text / Web disclosure	TAE1SOCPT
Template 23	Summary of subjects with at least one serious fatal unsolicited adverse event classified by MedDRA Primary System Organ Class and Preferred Term occurring from day of challenge until the end of challenge phase (Day 314) (Intention-to-treat set)	Post-text/ Web disclosure	TAE1SOCPT

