Total : n/%= number/percentage of subjects/doses with at least one local symptom whatever the number of injections.

95%CI= Exact 95% confidence interval; LL = lower limit, UL = upper limit

Template 22 Incidence of temperature by maximum value, within 7 days following each vaccination and overall (Intention-to-treat set)

	<Group 1>				<Group 2>			
	n	%	95% CI		n	%	95% CI	
			LL	UL			LL	UL
<Vaccination at visit 1> N	xxx				xxx			
≥37.5								
.....								
<39.0	xxx	xx.x	xx.x	xx.x	xxx	xx.x	xx.x	xx.x
related	xxx	xx.x	xx.x	xx.x	xxx	xx.x	xx.x	xx.x
<39.0 related	xxx	xx.x	xx.x	xx.x	xxx	xx.x	xx.x	xx.x
<Vaccination at visit 2> ...								
...								
Per subject								
Per vaccination								

Template 23 Summary of <subjects with/ vaccinations followed by> at least one <serious/related/related serious/fatal> unsolicited adverse events <medically attended visits>, <within 30 days of any vaccination/ within 30 days of post-challenge period / from study start to 30 days post-challenge> (Intention-to-treat set)

Primary System Organ Class (CODE) Preferred Term (CODE)	<Group 1> N=XXXX				<Group 2> N=XXXX			
	n	%	95% CI LL UL		n	%	95% CI LL UL	
Any <∅, serious, related, related serious, fatal> unsolicited adverse event <∅, - Medically Attended Visits>	xxx	xx.x	xx.x	xx.x	xxx	xx.x	xx.x	xx.x
<SOC 1 (code)>	xxx	xx.x	xx.x	xx.x	xxx	xx.x	xx.x	xx.x
<Preferred Term 1 (code)>	xxx	xx.x	xx.x	xx.x	xxx	xx.x	xx.x	xx.x
<Preferred Term 2 (code)>	xxx	xx.x	xx.x	xx.x	xxx	xx.x	xx.x	xx.x
...								
<SOC 2 (code)>	xxx	xx.x	xx.x	xx.x	xxx	xx.x	xx.x	xx.x
<Preferred Term 1 (code)>	xxx	xx.x	xx.x	xx.x	xxx	xx.x	xx.x	xx.x
<Preferred Term 2 (code)>	xxx	xx.x	xx.x	xx.x	xxx	xx.x	xx.x	xx.x
...								
...								

At least one symptom = At least one symptom experienced regardless of the System Organ Class
 N = Number of subjects having received at least one dose
 n/% = Number / percentage of subjects reporting at least once a specified symptom within 30 days after vaccination day 0 to day 29
 95% CI = Exact 95% confidence interval

Template 24 Summary of occurrences and subjects with at least one serious unsolicited adverse events from study start until last study visit (D314) (Intention-to-treat set)

Primary System Organ Class (CODE) Preferred Term (CODE)	<Group 1> N=XXXX			<Group xxx> N=XXXX		
	occ	n	%	occ	n	%
Any <∅, serious, related serious, fatal, related fatal> <∅, solicited and> unsolicited adverse event	xxx	xxx	xx.x	xxx	xxx	xx.x
<SOC 1 (code)>	xxx	xxx	xx.x	xxx	xxx	xx.x

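### Post-challenge AE and SAE percentages divide by all dosed vaccinees but only by challenged controls, so vaccine-arm rates would be diluted by about 20% (relative) at the planned drop-out

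*SAP*

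**What the plan says.** SAP 6.5.1 runs all safety analyses on the Intent-To-Treat Set (ITTS) and states that the "percentage of subjects reporting AEs after the sporozoite challenge will be tabulated by group and by MedDRA preferred term". SAP 5.1.2 defines the set differently for the two kinds of subject:

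- Vaccine arms: "The Intent-To-Treat Set (ITTS) will include all subjects who received at least one dose of study vaccine". Challenge is not required.
- Controls: "All challenged infectivity controls will also be included". Challenge is required.

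SAP 12.4 assigns Template 23 to the post-challenge AE tables, titled "Preferred Term within 30 days post- challenge (Intention-to-treat set)", and to the challenge-phase SAE tables, titled "occurring from day of challenge until the end of challenge phase (Day 314) (Intention-to-treat set)". Template 25 gives the AE category summary for the same 30 days, also on the ITTS. Template 23 in SAP 12.6.4 offers "within 30 days of post-challenge period" as one of its windows, but its footnote says "N = Number of subjects having received at least one dose" and counts events in the 30 days after vaccination.

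SAP 11.2.5 adds that for unsolicited AEs, SAEs and concomitant medication "all vaccinated subjects will be considered". Its table of denominators covers the vaccination phase only. Neither document gives a challenged-only denominator for any safety table.

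**The concern.** AEs in the 30 days from challenge are a listed secondary safety endpoint for the vaccinated groups and for the controls (SAP 4.2.3). A vaccinee without a challenge has no challenge date and so cannot contribute to the numerator, but under the stated rules stays in the denominator. Controls carry no such subjects.

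The error runs in one direction. Vaccine-arm rates look lower than they were among those at risk, which is also the direction a reader would expect from protection against malaria symptoms. If the share challenged differs between schedules, comparisons among the five vaccine arms are distorted too. The table of any post-challenge AE and the challenge-phase SAE tables are marked for web disclosure, so the diluted percentages would be public.

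**Working it through.** **Inputs**

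- 26 subjects per vaccine arm, at least 20 to be challenged, about 20% drop-out in vaccinees (Protocol 11.4).
- Withdrawals are not replaced (Protocol 10.2).
- Vaccine-arm N = all dosed; control N = all challenged (SAP 5.1.2, 11.2.5, Template 23).

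**The plan's own figure.** Enrolment needed for 20 challenged at 20% drop-out is 20 / (1 − 0.20) = 25. The protocol plans 26, which is consistent. Going forward, 26 × 0.80 = 20.8 challenged per arm.

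**Dilution.** With x subjects reporting an event, the table prints x / dosed, whereas the rate among those at risk is x / challenged. Their ratio is challenged / dosed, whatever x is, so the relative understatement is 1 − challenged / dosed. I take all 26 as dosed and all drop-out as falling between first dose and challenge.

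| Challenged of 26 | Factor | Relative understatement |
|---|---|---|
| 24 (assumed) | 0.923 | 7.7% |
| 21 | 0.808 | 19.2% |
| 20.8 (planned drop-out) | 0.800 | 20.0% |
| 20 (planned minimum) | 0.769 | 23.1% |
| 18 (assumed) | 0.692 | 30.8% |

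For controls, N is already the number challenged, so the factor is 1.

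**Effect on a printed row.** The event counts here are illustrative, because the documents give no expected AE rate.

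- 10 subjects with an AE: 10/26 = 38.5% (exact 95% CI 20.2 to 59.4) as written. With 20 challenged it is 10/20 = 50.0% (27.2 to 72.8); with 21 challenged, 10/21 = 47.6% (25.7 to 70.2).
- 15 subjects: 15/26 = 57.7% (36.9 to 76.6) against 15/20 = 75.0% (50.9 to 91.3).
- All 20 challenged subjects with an AE: 20/26 = 76.9% (56.4 to 91.0) against 20/20 = 100% (83.2 to 100).

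**The case against.** The best answer is that the challenge-phase denominator was left unspecified rather than set wrongly. Template 23 is a shared shell. Its footnote still carries a post-vaccination window, and read literally it gives controls, who receive no dose, N = 0. So it was plainly not adapted to the post-challenge tables. That explains how the text arose, but does not remove the problem: the ITTS definition and SAP 11.2.5 lead to the same vaccine-arm N without the footnote, and nothing in the SAP overrides them.

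Second, SAP section 7 calls all analyses descriptive, and Template 23 prints N, n, percentages and within-group intervals, with no between-group difference or p-value. The counts are shown, and the number not challenged can be found from the visit-attendance and disposition tables. This limits the harm, but the printed percentages and intervals would still be wrong.

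Several stronger inferences are tempting and should be resisted:

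- *A fixed gap in percentage points between vaccinees and controls.* The documents support only the relative factor; the gap depends on an AE rate they do not give.
- *The Day 286 to Day 314 SAE tabulation as a between-arm endpoint.* SAP 4.2.3 lists that endpoint for the control group only, although SAP 6.5.1 and 12.4 tabulate it by group. If its window is applied by study day, an unchallenged vaccinee could also contribute an SAE, so the dilution argument is firmest for AEs.
- *The same remedy for laboratory tables.* Template 29 carries the same dose-based footnote, but prints N at each timepoint. The first-parasitemia sample is event-driven, so challenged subjects who stay negative have none. Vaccinees who are not challenged remain in follow-up (Protocol 6.4.1.1), so restricting Day 314 laboratory tables to challenged subjects could discard valid data.
- *A wrong footnote on Template 30.* It has no denominator footnote; the difficulty there comes from SAP 11.2.5.

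**Conclusion.** The point stands for the post-challenge AE tables, for the challenge-phase SAE tables with the study-day caveat, and, through SAP 11.2.5, for challenge-phase concomitant medication. Followed as written, vaccine-arm percentages and exact intervals would be diluted relative to controls by about 20% in relative terms at the planned drop-out. The figure would be 23% with 20 of 26 challenged, and 8% to 31% over the assumed range of 24 to 18 challenged.

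The 20% is a planning value that the protocol itself calls approximate. The actual size depends on how many dosed subjects are challenged in each arm, and would be zero in an arm where all are. A reader might infer that the efficacy results are affected as well. They are not, because the per-protocol sets used for efficacy require challenge (SAP 5.1.4 and 5.1.5). The point is worth correcting before the tables are run, since the percentage and its interval are the whole result for this endpoint.

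**What to change.** - For the post-challenge AE and challenge-phase SAE tables (Templates 23 and 25) and for challenge-phase concomitant medication (Template 30), define N as ITTS subjects, vaccinated or control, who underwent sporozoite challenge. Elimination code 3000 in SAP 5.2 already identifies those who did not.
- In the Template 23 footnote for those tables, replace the dose-based N and the post-vaccination window with the challenged N and the window that applies (30 days from challenge, or challenge to Day 314). Leave the footnote as it is for the vaccination-window tables.
- In SAP 11.2.5, add a challenge-phase denominator alongside the vaccination-phase one.
- In Template 29, replace the dose-based footnote with N = subjects with a result at that timepoint. Do not restrict it to challenged subjects.

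The cost is a few lines of SAP wording and one denominator flag in the programs. No additional data are needed.
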